1. INTRODUCTION

1.1. Background & rationale

1.1.1. Treatment of schistosomiasis and the need for alternative drugs

Schistosomiasis is a chronic helminth infection that disproportionally affects poor and rural populations in sub-Saharan Africa, where it is almost exclusively caused by two species, *Schistosoma haematobium* (*Sh*) and/or *Schistosoma mansoni* (*Sm*). The transmission cycle requires contamination of surface water by excreta, specific freshwater snails as intermediate hosts, and human water contact. Infection occurs after *Schistosoma* larvae (cercariae) released by snails in surface water penetrate the host skin. These larvae then migrate in the tissues for about 5-7 weeks before developing in adult male and female worms in the veins, where they mate and start producing eggs.

Figure 1: Transmission cycle of schistosomiasis

Most morbidity and mortality associated with schistosomiasis results from organ lesions due to the host's immune response against schistosome eggs trapped in human tissues ¹. *Sh* causes primarily urogenital inflammation and scarring, leading to various complications, such as granulomatous cystitis, obstructive uropathy or infertility. In contrast, *Sm* affects mainly the intestines and liver, causing intestinal pseudopolyposis and periportal fibrosis with portal hypertension. Apart from "classic" pathologies, non-specific but disabling systemic morbidities, such as anemia, malnutrition and impaired physical and cognitive development, occur frequently ^{1–3}.

According to the most recent estimates of the Global Burden of Disease Study in 2016, schistosomiasis affects about 200 million people worldwide ⁴. In 2016, schistosomiasis accounted for approximately 10,000 deaths; 367,400 years of life lost; and 1,496,000 years lived with disability (YLDs) ^{4,5}. More than 90% of the global schistosomiasis burden is in sub-Saharan Africa, where the disease is among the top ten causes of YLDs ⁶.

In Senegal, both intestinal and urinary schistosomiasis are endemic, mainly in the north, the west and the south of the country. In the late 1980's, the northern region was confronted with a massive outbreak of *S. mansoni* infection, following the construction of the Diama dam on the Senegal River. Within a few years, the prevalence in Richard Toll, the epicenter of the epidemic went from 0% to almost 100%, with the highest intensities of infection ever described worldwide. Since then, the

infection rapidly spread throughout the northern region. A decade later, this severe *S. mansoni* epidemic was followed by a shift towards *S. haematobium* infection, which also reached record prevalences. Today, schistosomiasis is still highly endemic in Senegal, despite national control efforts. Both *S. mansoni* and *S. haematobium* are wide-spread, resulting in a large number of people with mixed infections in the communities ⁷.

Since the 1970s, treatment schistosomiasis has relied almost exclusively on praziquantel (PZQ). PZQ has demonstrated good efficacy ¹ in a meta-analysis of 55 comparative and non-comparative trials involving > 19,000 participants, of whom 68% were school-age children ⁸; results can be summarized as follows:

- For *Sh* infection, the WHO-recommended 40 mg/kg single dose of PZQ achieved a cure rate (CR) of 77.1% (95% confidence interval [CI] 68.4-85.1%; 2,645 participants/20 studies) and a mean egg reduction rate (ERR) of 94.1% (1,957 participants/19 studies).
- For *Sm* infection, the WHO-recommended 40 mg/kg single dose of PZQ achieved a CR of 76.7% (95% CI 71.9-81.2%; 6,377 participants/45 studies) and a mean ERR of 86.3% (5,546 participants/39 studies).
- For mixed Sh/Sm infection, CR was 63.5% (95% CI 48.2-77.0%; 379 participants/6 studies).

Another meta-analysis comparing school-age and preschool-age children in 47 comparative/noncomparative studies showed similar efficacy results in both age groups ⁹. The WHO has set a tentative ERR threshold of 90% as an indicator of optimal efficacy ¹⁰. In a systematic review of 10 studies, CR and ERR of *Sm* infection increased with repeated PZQ administrations, but such an effect was not observed for *Sh* ¹¹.

Thanks to its safety, efficacy and low cost, PZQ has become the mainstay of schistosomiasis control. It is the drug of choice for mass drug administration (MDA) programs targeting high risk groups, including school-age children. PZQ is administered at regular intervals with the aim of reducing parasite load and preventing severe disease (the so-called 'preventive chemotherapy')^{1,12}. Recommended time intervals between MDAs depends on the level of endemicity, but most of time PZQ is distributed annually to children 6 to 12 years of age, through school-based interventions. In 2015, PZQ has been distributed to 66.5 million of the estimated 218.8 million people requiring preventive chemotherapy worldwide, with a coverage of 42.2% in school-age children ¹³. This is supposed to further increase in the coming years to reach the target 75% coverage in this age group and to extend treatment to pre-school children ^{9,14}.

Despite the progress in schistosomiasis control attributed to preventive chemotherapy with PZQ, alternative therapeutics are urgently needed. The main reasons are 15,16 :

- PZQ is efficacious against all *Schistosoma* species, but only against the adult worms. Its activity against immature schistosome larvae is extremely weak, in the first few days up to 6-7 weeks after infection, before increasing progressively thereafter ^{17,18}. Treatment failures have usually been attributed to high reinfection rates by non-susceptible immature larvae, especially in high transmission areas, where large-scale and long-term use of PZQ monotherapy through repeated MDA in school-age children has not resulted in satisfactory community control so far ¹⁹.
- The extensive use of PZQ in monotherapy may result in the emergence of drug resistance ²⁰. PZQ resistance can be induced experimentally ^{21,22} and there have been sporadic reports on

¹ Efficacy is usually measured by the cure rate (CR: the proportion of egg-positive individuals, as assessed by urine and stool microscopy, who become egg-negative after treatment) and egg reduction rate (ERR: reduction of the post-treatment arithmetic and/or geometric mean egg count compared to pre-treatment mean count).

Schistosoma strains that have become tolerant or resistant, even though of little clinical relevance so far ^{23,24}. There is some recent evidence of a slow decrease of PZQ efficacy (below the ERR threshold of 90%) against *Sm* in Ugandan school-age children after increasing exposure to multiple MDA ²⁵. There is no guarantee that serious PZQ resistance will never appear ¹⁵.

Despite much exploratory research, no new compounds are close to reaching Phase 1 clinical evaluation in the coming years ^{16,18}. Therefore, current clinical research tends to concentrate on new PZQ-based regimens such as higher dosages, prolonged administration or repeated courses ¹⁴, or on repurposing drugs used against other diseases ¹⁶. So far however, most of the recently investigated drugs such as moxidectin, arachidonic acid or arterolane maleate/piperaquine have displayed unsatisfactory results, with ERRs far below the required 90% threshold ²⁶.

There is thus a need to further investigate alternative antischistosomal therapies. Two drugs widely used as antimalarial therapy have demonstrated *in vitro* and *in vivo* activity against *Schistosoma sp.*: artemisinin derivatives and mefloquine ^{27,28}.

- The antischistosomal effect of artemisinin-derivatives, such as artesunate and artemether has been studied since the 1980s in China. Adding artesunate/artemether to PZQ provides a superior efficacy against schistosomiasis, possibly due to the additional effect on immature larvae. In animal models, they showed excellent efficacy against the larval stages (> 90% reduction) and modest activity against adult worms (< 40% reduction)²⁹. In human studies in China, the cure rates of artemisinin derivatives against Schistosomiasis japonicum was 73-96% ³⁰, but such results could not be reproduced in Africa against *Sh* and *Sm*³¹. In three large clinical studies carried out in Africa on the effect of artesunate-based treatment on schistosomiasis, CR ranged from 14% to 59% and ERR from 35% to 93% ³¹. Artemisinin derivatives had higher efficacy than placebo, but usually lower than PZQ, even when multiple courses were administered ^{27,31}. However, adding artesunate or artemether to PZQ consistently provided higher cure rates than PZQ alone for each Schistosoma species studied (Sh: 265 participants/2 studies; Sm: 75 participants/1 study and S. japonicum: 196 participants/2 studies), with an aggregated odd ratio of 2.07 (95% CI 1.27-3.36; p= 0.003) ³². In addition, when artesunate and artemether were compared to placebo as chemoprophylactic agent against schistosomiasis, a significant protective effect was observed in all species, with an overall combined risk ratio of 0.11 (95% CI 0.06-0.22) and 0.25 (95% CI 0.16-0.40), respectively (P<0.001 for each). In a more recent study in Egypt, repeated administrations of artemether resulted in a substantial reduction of the incidence of new infections ³³.
- Mefloquine on the other hand displays strong activity against both larval and adult stages of *Sm* in mice ^{34,35} and the combination of mefloquine and PZQ was superior to either drug used alone in a mice model ³⁵. Only two small underpowered trials have evaluated the activity of mefloquine monotherapy against human schistosomiasis. Mefloquine alone appears less active than PZQ but cure rates increase with repeated administration. In the first exploratory phase 2 study ³⁶, a single course of mefloquine 25 mg/kg administered to 19 Ivorian schoolchildren infected with *Sh* (including 8 with *Sm* coinfection) had a lower efficacy than PZQ (ERR: 75% and CR: 21% versus 97% and 88% respectively). In the second preliminary trial ³⁷, two courses of mefloquine 15 mg/kg administered at one-month interval as intermittent preventive treatment against malaria to 30 Gabonese pregnant women with *Sh* infection resulted in an ERR of 80% after one course and of 98% after the second course, with a "final" CR of 47% at 6-week post-second course.

The combination artesunate-mefloquine (AM) is one of the five artemisinin-based combination therapies (ACTs) currently recommended by the WHO for the treatment of uncomplicated *Plasmodium falciparum (Pf)* malaria. A three-day course of AM consistently reaches cure rate above 95%. AM is the first-line treatment against *Pf* malaria for more than 15 years in many Latin American and Asian countries. Recently, AM has been developed as fixed drug combination (FDC) by the Drugs for Neglected Diseases initiative (DNDi) and is now manufactured at low price by Cipla (India) under two different co-formulations (for children and adults) that were pre-qualified by WHO in 2012.

The use of AM as antischistosomal therapy has however hardly been evaluated so far and results are contradictory and inconclusive. In the exploratory trial previously mentioned ³⁶, the efficacy of AM was similar to that of PZQ (ERR of 96% and CR of 61%). In another small (n=20/arm) exploratory trial in Ivorian schoolchildren with *Sh* infection ³⁸, adding mefloquine or AM to PZQ increased the ERR from 90 to 96% but not the CR (surprisingly low at 30% in all three arms). However, the sample size was not adequate to properly assess possible superiority.

Despite the *in vitro* and *in vivo* demonstration of activity of both drugs against larval and adult schistosomes, the benefit of the use of an AM combination in a clinical setting as an alternative antischistosomal therapy remains so far undetermined. It can be expected that in case of demonstrated dual activity of AM against malaria and schistosomiasis, clinical benefits would be even higher for patients with coinfection. Also, repeated administrations of AM, particularly during the rainy season when transmission of both schistosomiasis and malaria is highest, might have a cumulative effect not only on schistosomiasis and malaria morbidity but also on the rate of (asymptomatic) infections that is worth investigating. However, the risk of favoring resistance of malaria parasites has also to be scrutinized in co-endemic settings, even if this, as described above, seems extremely unlikely in the study area, the more when using a co-formulation at adequate antimalarial dosage.

1.1.2. Diagnosis of schistosomiasis and the need for alternative tools

Historically, schistosomiasis diagnosis has relied on the microscopic detection of *Schistosoma* eggs in urine or stool. The **Kato-Katz technique** is the standard method for assessing the prevalence and intensity of infection with *S. mansoni* in endemic countries, and **urine filtration** for the detection of urogenital infections due to *S. haematobium*. Both methods are relatively simple and inexpensive, almost 100% specific, and sufficiently sensitive to detect moderate and heavy *Schistosoma* infections. However, egg output strongly fluctuates and repeated examinations are needed to obtain an accurate assessment of infection. Moreover, light infections are easily missed, resulting in an underestimation of the true prevalence, particularly in low-prevalence settings, or inaccurate assessments of treatment efficacy ⁴⁸⁻⁵¹.

Treatment monitoring

With the current scaling up of MDA programs, the need for highly accurate diagnostic tools is evident. Highly sensitive diagnostic tools to detect light-intensity infections are pivotal for an accurate assessment of antischistosomal treatment response. Considerable progress has been made in recent years, and a number of promising novel tools have been developed, which are in different stages of innovation, standardization, validation or application. These new tools are either DNA- or antigenbased (see below):

- The past decade, the detection and quantification of *Schistosoma*-specific DNA in stool and urine samples using **real-time Polymerase Chain Reaction (PCR)** has proven to be a powerful tool for the accurate diagnosis of schistosomiasis ⁵². Specificity is virtually 100%, and sensitivities range from equal to, up to or substantially higher than, traditional microscopy techniques, the latter particularly in low-transmission settings and light-intensity infections ^{51,53,54}. Considering the high diagnostic accuracy and stability of real-time PCR over multiple time periods, the assay could be a valuable alternative to the current microscopic 'gold standard' for diagnosis of schistosome infections. Moreover, it can be run in a high through-put set-up, providing a valuable post-hoc diagnostic tool for clinical and epidemiological studies ^{54,55}. So far, data on the performance of real-time PCR as a monitoring tool after chemotherapy are limited⁵⁵. A major disadvantage of real-time PCR is that it requires expensive laboratory equipment and highly skilled personnel ⁵⁶. An interesting alternative could be the use of loop-mediated isothermal amplifications (LAMP) technology, which could be relatively easily adapted for field diagnosis in schistosomiasis-endemic areas ^{51,57-59}.
- Since 2008, a lateral flow immunochromatographic point-of-care (POC) test detecting *Schistosoma* circulating cathodic antigen (CCA) in urine has been developed and is now commercially available. This so-called **POC-CCA assay** is a rapid, user-friendly test designed for semi-quantitative field diagnosis of intestinal schistosomiasis. Accumulated evidence suggests that a single POC-CCA test is considerably more sensitive than conventional stool microscopy based on Kato–Katz for *S. mansoni* diagnosis, especially when infection intensities are low and after antischistosomal treatment ^{51,60–62}. The test has already shown its value as a diagnostic alternative for *S. mansoni* prevalence mapping in national control programs ^{62,63}. However, its suitability for measuring antischistosomal drug efficacy still needs to be investigated in more detail.
- Moreover, an up-converting phosphor lateral flow assay has recently been developed, which detects circulating anodic antigen (UCP-LF CAA) of all *Schistosoma* species in serum and urine at very low parasite loads, indicative of single worm infections ⁶⁴. Previous studies have indicated that circulating antigen levels are a better indication and more stable measure of schistosome worm burdens than egg counts ^{65,66}. Using urine as a non-invasive sample methodology, prevalence based on the UCP-LF CAA assay has recently shown to be three-fold higher than the prevalence detected with a single urine filtration ⁶⁷. This ultrasensitive test is currently being developed in a high-throughput rapid test format, which is already in development. The UCP-LF CAA technology, both under its current format or in its new rapid test version in development, still needs more validation in endemic settings, particularly in low-intensity areas and after treatment.

There is thus a need to define the utility of new methods, more sensitive than microscopy, in assessing treatment response.

Morbidity monitoring

Assessing schistosomiasis morbidity is usually done by **ultrasonography**. It is a well-established, widely accepted and accurate technique and is currently the diagnostic tool of choice for detecting organspecific lesions associated with chronic schistosomiasis (*S. haematobium*: urinary tract; *S. mansoni*: liver and spleen). ^{68,69}. Moreover, ultrasound examination (using portable machines) has proven to be feasible in operational research ⁷⁰. Field-applicable indirect tools are increasingly used to provide sensitive surrogate markers of *Sh* or *Sm* morbidity. Reagent strips for detecting **microhematuria** in urine are useful for the indirect diagnosis of *S. haematobium* infection and have since long been suggested as appropriate adjuncts for monitoring urogenital schistosomiasis morbidity ^{71,72}. More recently, two fecal point-of-care assays, namely **point-of-care fecal occult blood tests** and fecal calprotectin tests, have been proposed as simple, field-applicable instruments to demonstrate intestinal schistosomiasis ⁷³.

Further research is needed to evaluate the usefulness of these tests as field-adapted morbidity monitoring tools after antischistosomal treatment.

1.2. Hypothesis

Our research hypothesis is that through its combined effect on larval and adult schistosomes, the efficacy of one course of AM is at least similar to, and in case of repeated AM courses, higher than that of a standard PZQ treatment.

Secondly, we hypothesize that novel DNA- and antigen-based diagnostics are more accurate than conventional microscopy in assessing the actual antischistosomal treatment response.

2. STUDY OBJECTIVES

2.1. Primary objective

The primary objective of the **SchistoSAM** (**Schisto**somiasis **S**enegal **A**rtesunate-**M**efloquine) study is to evaluate the efficacy and safety of a single course of artesunate-mefloquine (AM, intervention arm) for the treatment of schistosomiasis in Senegalese primary school-age children, compared to the standard PZQ regimen (control arm).

Endpoint measures:

- Efficacy: Parasitological cure rate (CR, as assessed by microscopy, according to WHO standard) after administration of PZQ and after one AM course (at week 4 – see study flowchart).
- Safety: Frequency and pattern of drug-related adverse events (AEs) and serious AEs (SAEs) up to 4 weeks after PZQ and AM administration.

2.2. Secondary objectives

1. To evaluate the safety and cumulative efficacy of two additional courses of AM (at 6-week intervals each) for the treatment of schistosomiasis, compared to a single course of AM, and compared to the standard PZQ regimen (control arm).

Endpoint measures:

- Efficacy: CR, as assessed by microscopy, after the second and after the third AM administration (at week 10 and 16, 24 and 48 see study flowchart),
- Safety: Frequency and pattern of AEs and SAEs up to 4 weeks after the second and third AM administration.
- 2. To determine the egg reduction rate (ERR) obtained after single and repeated courses of AM compared to the standard PZQ regimen.
 - Endpoint measure: ERR after administration of PZQ and after each AM course (at week 4, 10, 16, 24 and 48 see study flowchart).
- 3. To determine the parasitological efficacy of single and repeated courses of AM by *Schistosoma* species and by infection intensity.

Endpoint measures: CR and ERR by initial *Schistosoma* infection intensity after PZQ administration and single and repeated courses of AM. (measured at week 4, 10 and 16 after first AM administration)

- 4. To assess the impact of repeated AM courses on schistosomiasis-related morbidity. Endpoint measures: Prevalence and severity of general and organ-specific schistosomiasis morbidity (as assessed by clinical evaluation, ultrasound, point-of-care morbidity markers and hemoglobin level) at week 24 and week 48 compared to baseline and compared to the control arm.
- To determine the diagnostic performance of novel schistosomiasis antigen- and DNA-based diagnostic assays to monitor antischistosomal treatment response.
 Endpoint measures: Sensitivity and specificity of the different conventional and novel diagnostic tests at baseline and at defined time points after treatment compared to conventional microscopy, and to composite reference standards.

6. To determine the effect of repeated AM courses on prevalence of *P. falciparum* infection as well as on incidence and morbidity of clinical malaria in school-age children with schistosomiasis.

Endpoint measures:

- Prevalence of malaria infection, as assessed by molecular testing of dried blood spots at baseline and week 24 and 48.
- Incidence of clinical malaria, as assessed by the number of incident malaria cases diagnosed through passive case detection during the study period (by standard malaria rapid tests and molecular diagnostics on dried blood spots).
- Frequency and severity of anemia, as assessed by determination of hemoglobin levels at baseline and at week 24 and 48 after initial treatment.
- To monitor the prevalence of Pf molecular markers associated with mefloquine resistance and the potential emergence of reduced artesunate susceptibility.

Endpoint measures:

- Prevalence and patterns of mutations in the K13 gene (for artemisinin susceptibility) and increased copy number of the Pfmdr1 gene or other relevant mutations (for mefloquine resistance) observed in the molecular surveys (baseline, week 24 and week 48).
- Presence and patterns of mutations observed in incident malaria cases.

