3. STUDY DESIGN

The **SchistoSAM** study is an open label, two-arm, individually-randomized controlled trial among infected primary school-age children in northern Senegal, with a non-inferiority design.

The study will take place during the rainy season (July-October) to maximize the potential benefits of repeated AM administrations on both schistosomiasis and malaria.

At baseline, prior to the first drug administration, all children fulfilling the study criteria (chapter 4.2) will undergo a full parasitological and morbidity assessment of:

- schistosomiasis infection: by microscopy (stool Kato-Katz and urine filtration) and point-of-care assays on site (POC-CCA) as well as additional diagnostics on preserved urine/stool samples (a UCP-LF CAA assay and a real time stool and urine PCR)
- 2. schistosomiasis systemic and organ-specific morbidity: by clinical evaluation, ultrasound, point-ofcare morbidity markers and hemoglobin level
- 3. malaria infection: by determination of prevalence through molecular testing on preserved blood samples, and prevalence/pattern of molecular markers of resistance
- 4. malaria morbidity: by measurement of proportion and severity of anemia

Subsequently, children will be randomized and assigned to one of the two following study arms:

- 5. **AM arm**: Three-day course of AM (A: 4 mg/kg and M: 8 mg/kg per day, given once a day for three days) administered at baseline and repeated twice at 6-week intervals (intervention).
- 6. **PZQ arm**: Single dose of PZQ (40 mg/kg) administered at study inclusion (control arm/standard of care).

The 6-weeks interval between AM administrations corresponds to the time lapse for larval maturation (from infection to adult worms). In addition, this 6-week period should minimize/prevent the risk of cumulative mefloquine-associated toxicity.

[figure not shown]
Parasitological assessments of schistosomiasis (urine and stool microscopy and POC-CAA) will take place in both arms at week 4, 10 and 16 after first administration of AM or PZQ. Full parasitological assessment of schistosomiasis and malaria (urine, stool and blood analysis) will be repeated at week 24 and 48 post-inclusion.

Morbidity assessment will be repeated as described here above at week 24 and 48 after initial treatment. These assessments are described in more detail in chapter 5.

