4.3. Sample size

The sample size was calculated on the parasitological cure rate endpoint after the first course of AM, to test the hypothesis that AM is non-inferior to PZQ: at least a 65% cure rate with AM as compared to a 75% cure rate with PZQ according to the following rationale. We consider that a cure rate (CR) of 65% is clinically acceptable as threshold for non-inferiority for the AM combination, for the following reasons: a cure rate above 65% would be very satisfactory compared to all alternative drugs evaluated so far against schistosomiasis, and an efficacy slightly lower than that of PZQ would be largely compensated by the positive clinical effect due to concomitant malaria suppression. Note that this is likely to be marginal in North Senegal where malaria transmission is low, but this "dual" effect could be a major added-value in many other co-endemic regions with higher malaria transmission

Sample size was calculated by simulation to obtain 80% power. The required sample size is 300 schoolchildren per arm. To account for a 20% loss to follow up, the total number of children to be recruited will be 726 (363 per arm). With the same sample size, superiority of repeated courses of AM to PZQ (cure rate of at least 85% after 3 courses) can also be demonstrated with a similar power (i.e. secondary endpoint).

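### Secondary objective 1 names a single AM course as efficacy comparator for added courses, but no child is randomised to stop after one, so that contrast is only a within-arm change from week 4

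*Protocol*

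**What the plan says.** Objective 1 in Protocol section 2.2 sets the two additional AM courses against two comparators in parallel: "for the treatment of schistosomiasis, compared to a single course of AM, and compared to the standard PZQ regimen (control arm". The synopsis repeats both. The efficacy endpoint is "CR, as assessed by microscopy, after the second and after the third AM administration", read at weeks 10, 16, 24 and 48.

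Section 3 gives the design: "Subsequently, children will be randomized and assigned to one of the two following study arms". The AM course is "administered at baseline and repeated twice at 6-week intervals (intervention". The control is "Single dose of PZQ (40 mg/kg) administered at study inclusion (control arm/standard of care". Microscopy "will take place in both arms at week 4, 10 and 16 after first administration of AM or PZQ", and again at weeks 24 and 48.

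For repeated courses, section 4.3 gives one power statement: superiority over PZQ, with a "cure rate of at least 85% after 3 courses".

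**The concern.** Objective 1 lists the single AM course on the same footing as the randomised control. A reader would expect a group treated once and followed over the same weeks, and there is none.

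The substitute is the same children at week 4, and their status can change after week 4 for reasons unrelated to courses 2 and 3. The protocol describes several of these reasons itself. A difference between week 4 and week 16 could then be taken as the gain from extra courses, or its absence as evidence that they add nothing. The design separates neither from the passage of time.

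**Working it through.** **What the design provides**

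| Reading | AM courses so far | Weeks since start of latest AM course | Randomised comparator at that visit |
|---|---|---|---|
| Week 4 | 1 | 4 | PZQ |
| Week 10 | 2 (second at week 6) | 10 − 6 = 4 | PZQ |
| Week 16 | 3 (third at week 12) | 16 − 12 = 4 | PZQ |
| Week 24 | 3 | 24 − 12 = 12 | PZQ |
| Week 48 | 3 | 48 − 12 = 36 | PZQ |

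Sources: sections 3 and 5.1. No row offers a single-course AM comparator at week 10 or later. At weeks 24 and 48 the time since treatment also differs from that at week 4.

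**Substitutes within the data.** Under section 6.1, children who do not receive full treatment stay in follow-up. Any child who stops after one course is self-selected, however. Section 8.3.1 also removes such children from the per-protocol set, which is the primary approach.

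**What changes with time, by the protocol's own account**
- Section 1.1.1 puts larval migration at about 5 to 7 weeks before worms mature and lay eggs. It also reports that PZQ failures are usually put down to reinfection in high-transmission areas.
- Section 3 places the courses in the season of transmission: "The study will take place during the rainy season (July-October) to maximize the potential benefits of repeated AM administrations".
- Section 1.1.2 says that egg output fluctuates strongly and that microscopy misses light infections, so a child's status can shift between visits in either direction.

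**What is sized.** Section 4.3 states 300 per arm. With a true cure rate of 75% in both arms, a 10-point margin, one-sided alpha 0.025 and 80% power:

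n = (1.960 + 0.842)² × (2 × 0.75 × 0.25) / 0.10² ≈ 7.85 × 0.375 / 0.01 ≈ 295 per arm.

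This reproduces the stated figure closely. It does so with an AM rate of 75%; the 65% in section 4.3 is the non-inferiority threshold. For 85% against 75% at 300 per arm, the power of a two-sided 5% test is 0.867. Both calculations concern AM against PZQ. Nothing is sized for three AM courses against one.

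**Direction of the bias.** Let c be the AM cure rate at week 4. Suppose no further drug were given. Let r be the share of egg-free children who would be egg-positive at week 16, and s the share of egg-positive children who would be egg-negative then.

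- Single-course cure rate at week 16: c(1 − r) + (1 − c)s.
- Before-after gain minus the gain over a concurrent single-course group: (1 − c)s − c·r.
- With c = 0.75: 0.25s − 0.75r, which is zero at s = 3r.

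The before-after change overstates the gain if s exceeds 3r and understates it if s is below 3r. The protocol gives neither r nor s, so sign and size stay open.

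**The case against.** The best defence is that the protocol never builds an inference on three courses against one. The hypotheses in sections 1.2 and 8.1, the power statement in section 4.3 and the main output described in section 12 all compare AM with PZQ. This stands. A reader might infer from objective 1 that the trial is set up to claim that three courses beat one; the rest of the protocol does not support that reading.

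Second, there is a concurrent control. Both arms are read at the same weeks, and section 8.3.4 plans a confidence interval for the difference in cure rates at each time point. The PZQ arm shows part of the time trend. This also stands, but only in part. Section 1.1.1 calls PZQ activity against immature larvae extremely weak, while section 1.2 assumes that AM acts on larvae. The PZQ trend is therefore not what children given one AM course would show. A treatment-by-visit term would compare AM with PZQ over time and would not supply the missing group.

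Third, the objective concerns cumulative efficacy. Weeks 4, 10 and 16 each fall four weeks after the start of a course, and the 6-week spacing was chosen to match larval maturation, so clearing newly matured worms is part of what repetition is for. That makes the within-arm change a fair description, but does not make it an estimate of three courses against one.

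Finally, labelling might be left to the analysis plan. The objective and the arms are fixed in the protocol, and an analysis plan cannot add a comparator.

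**Conclusion.** The point holds for one part of one secondary objective. The single-course efficacy comparison can only be a within-arm, non-randomised change from week 4, and objective 1 does not say so. This follows from the arms and visit schedule alone and needs no assumed rates.

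Two stronger readings should be resisted. A reader might infer a size by setting the 65% in section 4.3 against the 85% after three courses. But 65% is the non-inferiority threshold, not an expected AM cure rate, and the protocol gives no relapse or late-clearance rates after one course, so any figure for the bias would be invented. A reader might also infer that the repeated-AM hypothesis is compromised. It is not: repeated AM against PZQ is randomised, with both arms read at the same visits.

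**What to change.** In section 2.2, objective 1, and in the matching synopsis line, restate the single-course efficacy comparison as: *within-arm, non-randomised change in cure rate in the AM arm from week 4 to weeks 10 and 16 (descriptive)*. Show it beside the PZQ arm's change over the same visits and the randomised AM-PZQ differences at weeks 4, 10 and 16.

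Add that the confirmatory comparison of repeated AM is with PZQ only, and that the within-arm change will not be read as the causal gain of three courses over one. A ban on any comment on the within-arm change is not needed.

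The cost is a rewording in two places, with no extra children, visits or data. The sponsor gives up a three-versus-one claim that this design cannot support.
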